## **2. Rationale**

### **2.1. Justification of the relevance of the trial.**

Preterm birth complicates 13% of all pregnancies worldwide and is the most important cause of neonatal morbidity and mortality. Although disability-free survival rates have increased over the years as a result of improved facilities and treatments, preterm birth is still accountable for 75% of all perinatal deaths and >50% of morbidities. Women with a history of a preterm delivery have a distinctly increased risk to deliver preterm in a subsequent pregnancy. This risk ranges from 11,1% with one previous preterm delivery up to 28% for two previous preterm deliveries. This also applies to women with a history of a second trimester fetal-loss after 20 weeks of gestation who show an increased risk of 12% for preterm birth in a subsequent pregnancy. Yet another independent risk factor for PTB is a previous cervical surgery; after a single surgical conisation the risk of PTB increases almost 5 fold and after two even 10-fold. One treatment option for prevention of preterm birth is a cervical pessary. A cervical pessary is a silicone ring with a smaller diameter to be fitted around the cervix and a larger diameter to fix the device against the pelvic floor. This effectively rotates the cervix toward the posterior vaginal wall and corrects the cervical angle. A prospective-randomised trial by Goya et. al proved a significant reduction of the preterm delivery rate in singleton pregnancies with cervical shortening ( $\leq 25$  mm, 18-22 weeks of gestation) after placement of a pessary compared to expectant management. In a cohort analysis by Alfirevic et al. of asymptomatic women with a singleton pregnancy and a history of preterm birth and a short sonographic cervix the placement of a cervical pessary proved to be as effective as cerclage or treatment with 200 mg vaginal progesterone in reducing the preterm birth rate. A pilot study investigating the effect of pessary treatment in asymptomatic women with a singleton pregnancy and a history of at least one cold knife conisation and a short sonographic cervix suggest a beneficial effect on the prolongation of the pregnancy. In the one Cochrane review available concerning pessary therapy the authors detail a significant decrease in the incidence of spontaneous preterm birth in women with a short cervix when compared with expectant management: PTB less than 37 weeks'

gestation (22% versus 59 %; RR 0.36, 95% CI 0.27 to 0.49) and PTB less than 34 weeks' gestation (6% and 27% resp. RR 0.24; 95% CI 0.13 to 0.43). However, the need for further trials in different settings and with different risk factors is obvious. This study aims to investigate the effect of a prophylactic treatment with a cervical pessary in women at high risk of PTB due to a history of at least one previous preterm delivery and/or a history of late abortion.

## **2.2. Description of the study population.**

Women with a singleton pregnancy at 12 – 18 weeks of gestation and a history of at least one previous preterm delivery before 34+0 weeks and/or a history of late abortion attending the reference hospital and who do not fulfil the exclusion criteria the study will be proposed. The patients will be informed of the intended therapeutic effect and possible side effects. If they agree and after obtaining their informed consent, they will be randomised according to either usual management with rescue cerclage placement only when (and as soon as possible) a cervical shortening below 25 mm occurs (=control group) or cervical pessary placement (= pessary group). Pessaries or cerclage shall be placed up to 37+0 weeks of gestation. Serial cervical length measurements shall be conducted every 4 weeks in order to diagnose cervical shortening as soon as possible in the control group.

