#### 4.2. Description of the trial design.

Open Multicentre Randomized Controlled Trial, in parallel groups, based on treatment with progesterone comparing the placement of a prophylactic cervical pessary with usual management in singleton pregnancies at high-risk of PTB due to a history of at least one previous preterm delivery and/or a history of late abortion.

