#### 4.3. Flowchart.

#### 4.4. Description of the medical device and the treatment regimen.

The cervical pessary is a vaginal device (silicone ring) that is used to treat pregnant women for preventing spontaneous preterm birth. This device can be easily placed around the uterine cervix without pain (see annex I).

Women with a singleton pregnancy at 12+0 – 18+0 weeks of gestation and a history of at least one previous preterm delivery before 34+0 weeks and/or a history of late abortion attending the reference hospital for a preventive examination will be informed of the ongoing trial. The patient will be advised of the intended therapeutic effect and possible side effects. If they agree and after obtaining their informed consent, they will be randomised according to either progesterone (=control group) or cervical pessary placement up to 37+0 weeks (= pessary group).

If the pregnant woman is assigned to the pessary group and after having excluded a vaginal infection the pessary will be inserted directly. This procedure does not need anaesthesia and it does not need to be done in a surgery room. After the insertion of the pessary the correct fit of the pessary is verified by transvaginal ultrasound and in case it does not fit perfectly, it can easily be adjusted.

In the control-group, the pregnant women be treated with progesterone. Utrogestan is one of the normal drugs in China to prevent spontaneous preterm birth, the Utrogestan used in this study is from Laboratories Besins International. For the enrollment, pregnant women in the control group were treated by 200 mg QN, it is used for 34 gestational weeks.

The pessary will be removed at 37+0 weeks of gestation, or before if any unexpected event occurs (see 4.6). After insertion of the pessary the obstetrical management during the remainder of the pregnancy will be usual management.

Further surveillance of the pregnancy will not be influenced by the participation on the study.

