#### **4. 10. 4. Rescue treatment criteria.**

According the current guide and expert advice, when the routine follow-up examination, the rescue cervical cerclage may be adopted when the secondary cervical shortening occurs.

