#### **4.11. Treatment of Subjects**

##### **4.11.1. Treatments to be administered.**

The pessary will be inserted during a preventive examination in pregnancy in the examination room. This procedure does not need anaesthesia and it does not need to be done in a surgery room. After the insertion of the pessary the correct fit of the pessary is verified by transvaginal ultrasound and in case it does not fit perfectly, it can easily be adjusted. pregnant women in the control group were treated by 200 mg QN, it is used for 34 gestational weeks. The pessary or cerclage will be removed at 37+0 weeks of gestation, or before if any unexpected event occurs (see 4.6).

After insertion of the pessary the obstetrical management during the pregnancy will be usual management.

Further surveillance of the pregnancy will not be influenced by the participation on the study.

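### The two arms are not defined consistently: controls get usual management with rescue cerclage in one section and progesterone in others, and whether the pessary arm gets progesterone is left open

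*Protocol*

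**What the plan says.** The protocol describes the randomised treatments in several places.

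- **Section 2.2** assigns controls to "usual management with rescue cerclage placement only when (and as soon as possible) a cervical shortening below 25 mm occurs (=control group"). Progesterone does not appear. The same section adds: "Serial cervical length measurements shall be conducted every 4 weeks in order to diagnose cervical shortening as soon as possible in the control group".
- **Section 4.2** describes the design as "based on treatment with progesterone comparing the placement of a prophylactic cervical pessary with usual management".
- **Section 4.4** states that "they will be randomised according to either progesterone (=control group) or cervical pessary placement up to 37+0 weeks (= pessary group"), and then: "In the control-group, the pregnant women be treated with progesterone". It calls Utrogestan one of the drugs normally used in China for this purpose. For the pessary arm it says: "After insertion of the pessary the obstetrical management during the remainder of the pregnancy will be usual management".
- **Section 4.11.1** repeats the control regimen: "pregnant women in the control group were treated by 200 mg QN, it is used for 34 gestational weeks". The drug is not named there; 4.4 supplies the name.
- **Section 4.10.4** says that "the rescue cervical cerclage may be adopted when the secondary cervical shortening occurs", naming neither an arm nor a length threshold.
- **Section 6.2**: the schedule labels pessary placement as applying to the pessary group. The progesterone row carries no arm label.
- **Section 7.2** plans on 0.80 in the control group and 0.924 in the treatment group, without saying which control regimen the 0.80 refers to.

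**The concern.** Sections 2.2 and 4.4 each define the same randomisation, and they name different control treatments. The pessary arm's progesterone status is also unsettled, because the signals conflict within and between sections.

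The contrast between arms is the question the trial asks. This is an open, multicentre trial, so each site will deliver what it understands the text to require. If some sites give progesterone to the pessary arm and others do not, or if controls differ in progesterone or access to cerclage, the pooled estimate mixes different comparisons. Analysis cannot separate them afterwards unless the intended regimen was fixed beforehand.

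**Working it through.** **Step 1. Set the definitions side by side.**

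| Section | Control arm | Pessary arm |
|---|---|---|
| 2.2 | Usual management; cerclage if cervix shortens below 25 mm; progesterone not mentioned | Pessary |
| 4.2 | Usual management, in a trial based on progesterone | Pessary, in a trial based on progesterone |
| 4.4 | Progesterone | Pessary as the alternative to progesterone; usual management after insertion |
| 4.11.1 | 200 mg regimen | Pessary; usual management after insertion; no drug regimen stated |
| 4.10.4 | Cerclage permitted, arm not named, no threshold | Same sentence, arm not named |
| 6.2 | Progesterone row, no arm label | Same row, no arm label |

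**Step 2. Try to merge them.** Suppose usual management includes progesterone. Then 2.2 and 4.4 agree for controls. But 4.4 and 4.11.1 also give the pessary arm usual management after insertion, so that arm would receive progesterone too. This fits 4.2 and the unlabelled row in 6.2, but contradicts the either/or wording in 4.4. Suppose instead that usual management excludes progesterone. Then 2.2 contradicts 4.4 on the control arm. Neither reading fits every section.

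**Step 3. Reproduce the figure in 7.2.** Inputs: 0.924 and 0.80, two-sided alpha 0.05, pooled-variance Z test, 80% power.

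- Mean proportion: (0.924 + 0.80)/2 = 0.862.
- n = [1.960·√(2·0.862·0.138) + 0.842·√(0.924·0.076 + 0.80·0.20)]² / 0.124² = (0.956 + 0.404)² / 0.01538 ≈ 120.3, so 121 per arm. This matches the protocol.
- Power at 121 per arm is 0.802.

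**Step 4. Compare the planned effect with the evidence in 2.1.** Section 7.2 names no outcome. I assume its proportions are event-free proportions. The implied event ratio is (1 − 0.924)/(1 − 0.80) = 0.076/0.20 = 0.38.

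- Against expectant management, 2.1 quotes births before 34 weeks of 6% and 27%, RR 0.24, 95% CI 0.13 to 0.43. The value 0.38 lies inside that interval.
- Against cerclage or 200 mg vaginal progesterone, 2.1 reports that the pessary did equally well. It gives no figure; I read this as a ratio near 1.

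The chance of a significant result with 121 per arm and control 0.80, where the pessary proportion is 1 − 0.20 × ratio:

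| Event ratio | Pessary proportion | Chance of significance |
|---|---|---|
| 0.24 | 0.952 | 0.953 |
| 0.38 | 0.924 | 0.802 |
| 0.43 | 0.914 | 0.719 |
| 1 | 0.800 | 0.05 (alpha) |

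**Step 5. Check whether a direction of power change can be claimed.** The protocol gives no other control rate, so the values below are assumptions. Entries are power at 121 per arm.

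| Assumed control | Pessary held at 0.924 | Ratio held at 0.38 | Difference held at 0.124 |
|---|---|---|---|
| 0.78 | 0.889 | 0.845 | 0.756 |
| 0.82 | 0.680 | 0.752 | 0.853 |
| 0.84 | 0.526 | 0.694 | 0.905 |

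The direction depends on what is held fixed, so no power loss follows from the documents.

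**The case against.** The best defence is that the control arm is less contradictory than it looks. Section 2.2 sits in the rationale, the two treatment sections (4.4 and 4.11.1) agree on progesterone for controls, and 4.4 calls the drug a normal one, so usual management can include it. Usual management after pessary insertion may simply mean routine obstetric care. The rescue-cerclage wording in 4.10.4 may differ from 2.2 only in detail, since 2.2 does not forbid cerclage in the pessary arm. The flowchart under 4.3 is not visible in the copy reviewed and might show the allocation.

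Much of this is fair. A site reading the whole protocol would probably give controls progesterone, and the rescue-cerclage point is supporting rather than central. But the merged reading leaves the pessary arm open: 4.2 and the unlabelled row in 6.2 point towards progesterone in both arms, while 4.4 and 4.11.1 point to controls only. A flowchart could show the intended allocation, but the contradictory sentences would remain.

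The numerical comparison is also open to challenge. Section 4.1.1 names birth and survival of the child as the primary outcome, so the 7.2 proportions may not describe preterm birth at all, and the ratios in 7.2 and 2.1 would then measure different things. Both cited comparisons concern women with a short cervix, and the comparison with cerclage and progesterone is a cohort analysis. These limits stand. The figures illustrate why the comparator must be named; they do not estimate this trial's power.

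**Conclusion.** The concern holds and should be corrected before the results can be interpreted. The contradiction rests on the text alone and needs no assumption: 2.2 and 4.4 define the control arm differently, and no single reading of usual management reconciles 2.2, 4.2, 4.4 and 4.11.1. Three different trials are compatible with the wording.

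The size cannot be expressed as a loss of power. What can be said is that the planned event ratio of 0.38 is of the order 2.1 reports against expectant management and far from the parity it reports against progesterone or cerclage. That comparison assumes that 7.2 refers to event-free proportions, on an outcome comparable with birth before 34 weeks, and that parity means a ratio near 1.

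**What to change.** Reconcile sections 2.2, 4.2, 4.4, 4.10.4 and 4.11.1, and the schedule in 6.2, into one definition of each arm that states:

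- which arm or arms receive progesterone;
- whether the serial cervical-length measurements apply to one arm or both;
- whether rescue cerclage applies to one arm or both, with a single statement on the threshold.

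State the tested contrast once in 4.2 and use the same terms throughout. In 7.2, say which control regimen the 0.80 describes and why a difference of 0.124 is expected against it, given what 2.1 reports for progesterone and cerclage. The choice of regimen and of any clinical threshold is the sponsor's.

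The cost is amendment wording, a clarification to sites, and one or two sentences in 7.2. If the comparator named is progesterone, the sponsor will also have to justify the planned difference against its own summary of the evidence.

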#### **4.6. Completion and interruption criteria of the study or the subjects.**

The pessary will be removed at 37+0 weeks of pregnancy. The indications to remove them before this time will be: active bleeding stronger than period bleeding, persistent contractions after tocolysis and premature rupture of the membranes after 34+0 weeks.

After removing the pessary, the obstetrical management will be done as usual and will not be influenced by the study.

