## **10. Data Management and Registry File**

Patient's participation in the study will be annotated into the medical history. The main investigator will perform a list with the participant's names, ID numbers and codes. He also will have a file with all the information referring to the study. All the data will be collected in a database that will be accessed worldwide. The randomisation will be done on a computer basis. Once entering in the website, if the patient fulfils the inclusion criteria, the computer generated list will randomise the patient to "pessary" or "control" group. The excluded patients will be also collected in the database. Every participating centre will have its own randomisation list, and it will be accessible with a username and password. The trial staff will ensure that the participants' anonymity is maintained. Only a participant ID number on the CRF and in the electronic database will identify the participants. All documents will be stored securely and only accessible by trial staff and authorized personnel. The study will comply with the Data Protection Legislation that requires data to be anonymized as soon as it is mandatory to do so.

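### The protocol does not secure equal cervical-length surveillance and rescue cerclage in the two arms: section 2.2 ties both to controls, while section 4.10.4 gives no threshold and names no arm

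*Protocol*

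**What the plan says.** Protocol section 2.2, which describes the study population, defines the control group as usual management with "rescue cerclage placement only when (and as soon as possible) a cervical shortening below 25 mm occurs". It defines the other group only by pessary placement. It then adds: "Serial cervical length measurements shall be conducted every 4 weeks in order to diagnose cervical shortening as soon as possible in the control group". It also says "Pessaries or cerclage shall be placed up to 37+0 weeks of gestation", which gives no end point for the scans.

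Section 4.10.4, under the heading of rescue treatment criteria, refers to current guidance, expert advice and routine follow-up, and says that "the rescue cervical cerclage may be adopted when the secondary cervical shortening occurs". It states no length in millimetres, no scan interval and no arm.

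Sections 4.4 and 4.11.1 say that obstetrical management after pessary insertion is usual management. Both add: "Further surveillance of the pregnancy will not be influenced by the participation on the study". Section 6.2 says that the women, without distinction by arm, are assessed as in usual high-risk care.

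Section 4.2 describes the trial as "Open Multicentre Randomized Controlled Trial, in parallel groups". Section 10 says "Every participating centre will have its own randomisation list".

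**The concern.** Cerclage is an active treatment against the outcome under study. Section 2.1 itself cites a cohort analysis in which pessary, cerclage and vaginal progesterone did about equally well in women with a previous preterm birth and a short cervix. How often a short cervix is looked for, and what happens once it is found, therefore bears on the result.

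Section 2.2 attaches an interval and a trigger to controls. No section states either for pessary women. Staff know the allocation. At a site that takes 2.2 literally, shortening would be sought every 4 weeks in controls and rescued by rule, while in pessary women detection would rest on routine follow-up and rescue on judgement. The pessary comparison at that site would then carry a difference in detection and cerclage as well.

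Scan frequency and rescue triggers are matters of trial conduct. They belong in the protocol and are not details to be left to an analysis plan.

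**Working it through.** The claim concerns procedures, so the main check sets the sections side by side.

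| Item | Control arm | Pessary arm |
|---|---|---|
| Scan interval | 4 weeks (2.2) | none stated; usual management (4.4, 4.11.1) |
| Rescue trigger in 2.2 | only below 25 mm, as soon as possible | none stated |
| Rescue rule in 4.10.4 | discretionary, no threshold, arm not named | same sentence, arm not named |

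Two readings fit this table.

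1. *Equal care.* Section 2.2 describes control care as a form of usual management, and 4.4 and 4.11.1 give pessary women usual management. If the term means the same thing in both places, both arms have the scans and the rescue.
2. *Unequal care.* The interval and the trigger belong to controls only, and pessary women come under 4.10.4 alone.

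No sentence decides between them, so the protocol does not secure equality. It does not prescribe inequality either.

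*Detection interval.* With scans 4 weeks apart, a short cervix in a control woman is found at most 4 weeks after it appears, and after 4/2 = 2 weeks on average. This assumes uniform onset between scans, every scan attended, no missed shortening and continued scanning. For pessary women under reading 2, no limit is stated.

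*How sensitive the design is (assumed shifts, not an estimate).* Inputs from 7.2: 121 per arm, proportions 0.924 and 0.800, two-sided pooled Z-test, alpha 5%.

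- Power = Φ[(d − 1.96·SE0)/SE1], with SE0 = √(2·p̄(1−p̄)/n) and SE1 = √([p1(1−p1)+p2(1−p2)]/n).
- The plan's own figure: d = 0.124, p̄ = 0.862, SE0 = 0.0443, SE1 = 0.0436. This gives Φ(0.85) = 0.802, so the stated 80% reproduces.
- If extra rescue raised the control proportion to 0.82, 0.84 or 0.86 with the pessary arm at 0.924, power would be 68%, 53% or 36%.
- If the pessary did nothing and rescue lifted controls alone from 0.80 by 2, 4 or 6 points, the two-sided rejection rate would be about 7%, 13% or 24% instead of 5%.

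The shifts of 2 to 6 points are chosen for illustration, and so is their direction. More discretionary cerclage in the pessary arm would push the other way.

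*Sites.* Because each centre has its own list, differences in practice between sites do not by themselves bias the comparison. Only a difference between arms within a site does.

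**The case against.** The strongest case on the other side has four parts.

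- **Section 2.2 is not the operative rule.** It describes the population within the rationale. The design section (4.4) gives controls progesterone and does not mention a scan-and-rescue strategy. If section 4 governs, 4.10.4 is the only rescue rule and does not distinguish the arms. This stands as a possible reading. But 2.2 is current text and the only place with an interval or a threshold, and 4.10.4 on its own leaves rescue to open-label discretion.
- **Usual management may already mean equal care.** This also stands as a possibility, and it is why the point is limited to what the text fails to secure. A reader might infer that the protocol requires unequal care, or that bias will occur. The documents do not support that.
- **A control-only strategy would be legitimate.** A randomised comparison of pessary with scan-and-rescue is valid for that question. This stands in full. The protocol would then need to say so, and the conclusion would have to match.
- **Evidence is incomplete.** The flowchart (4.3) and the case report form are not shown, and the blank vaginal ultrasound row in the 6.2 table may be an extraction loss. None of these is relied on here.

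Two further inferences are tempting. One is that a fixed 4-weekly scan contradicts the statement that surveillance is unaffected by participation. That holds only if such scans are not already usual care for these women, and the protocol does not say. The other starts from 4.6, where the early-removal indications are "active bleeding stronger than period bleeding, persistent contractions after tocolysis and premature rupture of the membranes after 34+0 weeks". Cerclage is not among them, and a reader might infer that the pessary must come out when a cerclage is placed. That silence supports no particular rule, and the choice is clinical.

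**Conclusion.** The point holds as a gap between current sections. Section 2.2 ties 4-weekly measurement and the below-25 mm cerclage rule to controls, 4.10.4 allows rescue without threshold or arm, and no section states the same schedule or trigger for pessary women. In an open trial, detection and rescue can therefore differ between arms within a site.

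The size and direction of any resulting bias cannot be computed. The protocol gives no rate of shortening, no rate of rescue and no effect of cerclage. The power and error figures above show sensitivity to assumed shifts and should not be quoted as expected losses. The conclusion rests on at least some sites taking 2.2 at its word, or using the discretion in 4.10.4 differently by arm. The clarification is worth making because it is cheap. The point disputes no sample-size figure.

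**What to change.** - In 4.10.4, define secondary cervical shortening as below 25 mm, taken from 2.2, and state that this is the threshold at which rescue cerclage may be considered in either arm. Cerclage need not become mandatory in pessary women.
- State there that cervical length is measured on the same schedule in both arms, and align 2.2 with it.
- Record cerclage and report it by arm. The case report form is not shown, so this may already be in place.
- If scan-and-rescue is meant for controls only, say so in 4.4 and 4.10.4 instead, and limit the conclusion to pessary versus that strategy.

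**Cost.** Protocol wording, and possibly one recorded item. Added scans in pessary women are none if 4-weekly measurement is already usual care. If it is not, the number per woman depends on when scanning stops, which 2.2 does not say:

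- to 37+0: (37−18)/4 = 4.75 to (37−12)/4 = 6.25, so 4 to 6 scans after entry;
- to 34+0: (34−18)/4 = 4 to (34−12)/4 = 5.5, so 4 to 5.

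Some rescue discretion remains. A difference between arms would become visible but would not be excluded, and cerclage in pessary women can change the treatment contrast.
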